10.3.5 Reporting of AEs, SAEs, and Other Reportable Safety Events to the Sponsor

AE, SAE, and other reportable safety event reporting to Sponsor via electronic data collection tool

- The primary mechanism for reporting to the Sponsor will be the electronic data collection (EDC) tool.
 - Electronic reporting procedures can be found in the EDC data entry guidelines (or equivalent).
 - If the electronic system is unavailable for more than 24 hours, then the site will use the paper AE Reporting form.
 - Reference Section 8.4.1 for reporting time requirements.
- The site will enter the SAE data into the electronic system as soon as it becomes available.
- After the study is completed at a given site, the EDC tool will be taken off-line to prevent the entry of new data or changes to existing data.
- If a site receives a report of a new SAE from a study participant or receives updated data on a previously reported SAE after the EDC tool has been taken off-line, then the site can report this information on a paper SAE form or by telephone (see next section).
- Contacts for SAE reporting can be found in the Investigator Study File Binder (or equivalent).

SAE reporting to the Sponsor via paper CRF

- If the EDC tool is not operational, facsimile transmission or secure e-mail of the SAE paper CRF is the preferred method to transmit this information to the Sponsor.
- In rare circumstances and in the absence of facsimile equipment, notification by telephone is acceptable with a copy of the SAE data collection tool sent by overnight mail or courier service.
- Initial notification via telephone does not replace the need for the investigator to complete and sign the SAE CRF pages within the designated reporting time frames.
- Contacts and instructions for SAE reporting and paper reporting procedures can be found in the Investigator Study File Binder (or equivalent).

10.4 Appendix 4: Device Events, Adverse Device Events, and Medical Device Incidents: Definitions, Collection, and Documentation

Not applicable

10.5 Appendix 5: Contraceptive Guidance and Pregnancy Testing

10.5.1 Definitions

Women of Childbearing Potential (WOCBP)

A woman is considered fertile following menarche and until becoming postmenopausal unless permanently sterile (see below).

If fertility is unclear (eg, amenorrhea in adolescents or athletes) and a menstrual cycle cannot be confirmed before first dose of study intervention, additional evaluation should be considered.

Women in the following categories are not considered WOCBP:

- Premenarchal
- Premenopausal female with 1 of the following:
 - Documented hysterectomy
 - Documented bilateral salpingectomy
 - Documented bilateral oophorectomy

For individuals with permanent infertility due to an alternate medical cause other than the above (eg, Mullerian agenesis, androgen insensitivity), investigator discretion should be applied to determining study entry.

Note: Documentation can come from the site personnel's review of the participant's medical records, medical examination, or medical history interview.

- Postmenopausal female
 - A postmenopausal state is defined as no menses for 12 months without an alternative medical cause.
 - A high follicle stimulating hormone (FSH) level in the postmenopausal range may be used to confirm a postmenopausal state in women not using hormonal contraception or hormone replacement therapy (HRT). However, in the absence of 12 months of amenorrhea, confirmation with two FSH measurements in the postmenopausal range is required.
 - Females on HRT and whose menopausal status is in doubt will be required to use one of the nonhormonal highly effective contraception methods if they wish to continue their HRT during the study. Otherwise, they must discontinue HRT to allow confirmation of postmenopausal status before study enrollment.

10.5.2 Contraception Requirements

Contraceptives allowed during the study include ^a:
Highly Effective Contraceptive Methods That Have Low User Dependency Failure rate of <1% per year when used consistently and correctly.

● Progestogen-only subdermal contraceptive implant ^{b,c}● Intrauterine hormone-releasing system (IUS) ^{c,d}● Intrauterine device (IUD)● Bilateral tubal occlusion

● Azoospermic partner (Vasectomized or secondary to medical cause) This is a highly effective contraception method provided that the partner is the sole male sexual partner of the WOCBP and the absence of sperm has been confirmed. If not, an additional highly effective method of contraception should be used. A spermatogenesis cycle is approximately 90 days. Note: Documentation of azoospermia can come from the site personnel's review of the participant's medical records, medical examination, or medical history interview.
Sexual Abstinence 
● Sexual abstinence is considered a highly effective method only if defined as refraining from heterosexual intercourse during the entire period of risk associated with the study treatment. The reliability of sexual abstinence needs to be evaluated in relation to the duration of the study and the preferred and usual lifestyle of the participant.
a.) Contraceptive use by men or women should be consistent with local regulations regarding the use of contraceptive methods for participants of clinical studies. b.) If locally required, in accordance with Clinical Trial Facilitation Group (CTFG) guidelines, acceptable contraceptive implants are limited to those which inhibit ovulation. c.) Male condoms must be used in addition to the hormonal contraception. d.) IUS is a progestin releasing IUD. Note: The following are not acceptable methods of contraception: 
- Periodic abstinence (calendar, symptothermal, post-ovulation methods), withdrawal (coitus interruptus), spermicides only, and lactational amenorrhea method (LAM).- Male condom with cap, diaphragm, or sponge with spermicide.- Male and female condom should not be used together (due to risk of failure with friction).

10.6 Appendix 6: Collection and Management of Specimens for Future Biomedical Research

1. Definitions

- a. Biomarker: A biological molecule found in blood, other body fluids, or tissues that is a sign of a normal or abnormal process or of a condition or disease. A biomarker may be used to see how well the body responds to a treatment for a disease or condition.¹
- b. Pharmacogenomics: The investigation of variations of DNA and RNA characteristics as related to drug/vaccine response.²
- c. Pharmacogenetics: A subset of pharmacogenomics, pharmacogenetics is the influence of variations in DNA sequence on drug/vaccine response.²
- d. DNA: Deoxyribonucleic acid.
- e. RNA: Ribonucleic acid.

2. Scope of Future Biomedical Research

The specimens consented and/or collected in this study as outlined in Section 8.9 will be used in various experiments to understand:

- The biology of how drugs/vaccines work
- Biomarkers responsible for how a drug/vaccine enters and is removed by the body
- Other pathways drugs/vaccines may interact with
- The biology of disease

The specimen(s) may be used for future assay development and/or drug/vaccine development.

It is now well recognized that information obtained from studying and testing clinical specimens offers unique opportunities to enhance our understanding of how individuals respond to drugs/vaccines, enhance our understanding of human disease and ultimately improve public health through development of novel treatments targeted to populations with the greatest need. All specimens will be used by the Sponsor or those working for or with the Sponsor.

3. Summary of Procedures for Future Biomedical Research.

- a. Participants for Enrollment

All participants enrolled in the clinical study will be considered for enrollment in future biomedical research.

b. Informed Consent

Informed consent for specimens (ie, DNA, RNA, protein, etc.) will be obtained during screening for protocol enrollment from all participants or legal guardians, at a study visit by the investigator or his or her designate. Informed consent for future biomedical research should be presented to the participants on the visit designated in the SoA. If delayed, present consent at next possible Participant Visit. Consent forms signed by the participant will be kept at the clinical study site under secure storage for regulatory reasons.

A template of each study site's approved informed consent will be stored in the Sponsor's clinical document repository.

c. eCRF Documentation for Future Biomedical Research Specimens

Documentation of participant consent for future biomedical research will be captured in the eCRFs. Any specimens for which such an informed consent cannot be verified will be destroyed.

d. Future Biomedical Research Specimen(s)

Collection of specimens for future biomedical research will be performed as outlined in the SoA. In general, if additional blood specimens are being collected for future biomedical research, these will usually be obtained at a time when the participant is having blood drawn for other study purposes.

4. **Confidential Participant Information for Future Biomedical Research**

In order to optimize the research that can be conducted with future biomedical research specimens, it is critical to link participant' clinical information with future test results. In fact little or no research can be conducted without connecting the clinical study data to the specimen. The clinical data allow specific analyses to be conducted. Knowing participant characteristics like gender, age, medical history and intervention outcomes are critical to understanding clinical context of analytical results.

To maintain privacy of information collected from specimens obtained for future biomedical research, the Sponsor has developed secure policies and procedures. All specimens will be single-coded per ICH E15 guidelines as described below.

At the clinical study site, unique codes will be placed on the future biomedical research specimens. This code is a random number which does not contain any personally identifying information embedded within it. The link (or key) between participant identifiers and this unique code will be held at the study site. No personal identifiers will appear on the specimen tube.

5. Biorepository Specimen Usage

Specimens obtained for the Sponsor will be used for analyses using good scientific practices. Analyses utilizing the future biomedical research specimens may be performed by the Sponsor, or an additional third party (eg, a university investigator) designated by the Sponsor. The investigator conducting the analysis will follow the Sponsor's privacy and confidentiality requirements. Any contracted third party analyses will conform to the specific scope of analysis outlined in future biomedical research protocol and consent. Future biomedical research specimens remaining with the third party after specific analysis is performed will be reported to the Sponsor.

6. Withdrawal From Future Biomedical Research

Participants may withdraw their consent for future biomedical research and ask that their biospecimens not be used for future biomedical research. Participants may withdraw consent at any time by contacting the principal investigator for the main study. If medical records for the main study are still available, the investigator will contact the Sponsor using the designated mailbox ([contact]). Subsequently, the participant's specimens will be flagged in the biorepository and restricted to main study use only. If specimens were collected from study participants specifically for future biomedical research, these specimens will be removed from the biorepository and destroyed. Documentation will be sent to the investigator confirming withdrawal and/or destruction, if applicable. It is the responsibility of the investigator to inform the participant of completion of the withdrawal and/or destruction, if applicable. Any analyses in progress at the time of request for withdrawal/destruction or already performed prior to the request being received by the Sponsor will continue to be used as part of the overall research study data and results. No new analyses would be generated after the request is received.

In the event that the medical records for the main study are no longer available (eg, if the investigator is no longer required by regulatory authorities to retain the main study records) or the specimens have been completely anonymized, there will no longer be a link between the participant's personal information and their specimens. In this situation, the request for withdrawal of consent and/or destruction cannot be processed.

7. Retention of Specimens

Future biomedical research specimens will be stored in the biorepository for potential analysis for up to 20 years from the end of the main study. Specimens may be stored for longer if a regulatory or governmental authority has active questions that are being answered. In this special circumstance, specimens will be stored until these questions have been adequately addressed.

Specimens from the study site will be shipped to a central laboratory and then shipped to the Sponsor-designated biorepository. If a central laboratory is not utilized in a particular study, the study site will ship directly to the Sponsor-designated biorepository. The specimens will be stored under strict supervision in a limited access facility which

operates to assure the integrity of the specimens. Specimens will be destroyed according to Sponsor policies and procedures and this destruction will be documented in the biorepository database.

8. Data Security

Databases containing specimen information and test results are accessible only to the authorized Sponsor representatives and the designated study administrator research personnel and/or collaborators. Database user authentication is highly secure, and is accomplished using network security policies and practices based on international standards to protect against unauthorized access.

9. Reporting of Future Biomedical Research Data to Participants

No information obtained from exploratory laboratory studies will be reported to the participant, family, or physicians. Principle reasons not to inform or return results to the participant include: Lack of relevance to participant health, limitations of predictive capability, and concerns regarding misinterpretation.

If important research findings are discovered, the Sponsor may publish results, present results in national meetings, and make results accessible on a public website in order to rapidly report this information to doctors and participants. Participants will not be identified by name in any published reports about this study or in any other scientific publication or presentation.

10. Future Biomedical Research Study Population

Every effort will be made to recruit all participants diagnosed and treated on Sponsor clinical studies for future biomedical research.

11. Risks Versus Benefits of Future Biomedical Research

For future biomedical research, risks to the participant have been minimized and are described in the future biomedical research informed consent.

The Sponsor has developed strict security, policies, and procedures to address participant data privacy concerns. Data privacy risks are largely limited to rare situations involving possible breach of confidentiality. In this highly unlikely situation, there is risk that the information, like all medical information, may be misused.

12. Questions

Any questions related to the future biomedical research should be emailed directly to [contact].

13. References

1. National Cancer Institute [Internet]: Available from <https://www.cancer.gov/publications/dictionaries/cancer-terms?cdrid=45618>

10.7 Appendix 7: Country-specific Requirements

Not applicable

10.8 Appendix 8: Blood Volume Table

Panel A (Part 1 and 2)	Pre-study	Treatment Periods	Post-study	Total Collections	mL Per Collection	Total mL/ Test ^a
Laboratory Safety Tests	1	9	1		5.0	55
HIV/Hepatitis Screen (at the discretion of the investigator)	1*			1	5*	5
Serum βHcg (if applicable)	1*		1	1	5	5
FSH (if applicable)	1*			See footnote		
PT aPTT	1	9	1	11	5	55
Mixed Venous Oxygen		8		8	5	40
Blood for Planned Genetic Analysis		1		1	8.5	8.5
Blood for MK-5475		43		43	6 mL	258
* Pre-study HIV/Hepatitis Screen, FSH and Serum HcG will be assayed from a single 5 mL blood sample						Female:~426.5mL
Total Blood Volume is for participants from Part 1 and continue into Part 2						Male: 421.5 mL
^a If additional pharmacokinetic/pharmacodynamic and/or safety analysis is necessary, additional blood (up to 50 mL) may be obtained. Note: never to exceed 50 mL.						

Panel A (Part 1 only)	Pre-study	Treatment Periods	Post-study	Total Collections	mL Per Collection	Total mL/ Test
Laboratory Safety Tests	1	6	1	8	5.0	40
HIV/Hepatitis Screen (at the discretion of the investigator)	1*			1	5*	5
Serum βHcg (if applicable)	1*		1	1	5	5
FSH (if applicable)	1*			See footnote	-	-
PT aPTT	1	6	1	8	5	40
Blood for Planned Genetic Analysis		1		1	8.5	8.5
Blood for MK-5475		30		30	6 mL	180
* Pre-study HIV/Hepatitis Screen, FSH and Serum HcG will be assayed from a single 5 mL blood sample						Female:~278.5 mL ^a
						Male:273.5 mL ^a
^a If additional pharmacokinetic/pharmacodynamic and/or safety analysis is necessary, additional blood (up to 50 mL) may be obtained. Note: never to exceed 50 mL.						

Panel B and C	Pre-study	Treatment Periods	Post-study	Total Collections	mL Per Collection	Total mL/ Test
Laboratory Safety Tests	1	5	1	7	5	35
HIV/Hepatitis Screen (at the discretion of the investigator)	1*			1	5	5
Serum βHcg (if applicable)	1*		1	1	5	5
FSH (if applicable)	1*			See footnote	-	-
PT aPTT	1	5	1	7	5	35
Mixed Venous Oxygen		8		8	5	40
Blood for Planned Genetic Analysis		1		1	8.5	8.5
Blood for MK-5475		23		23	6 mL	138
* Pre-study HIV/Hepatitis Screen, FSH and Serum HcG will be assayed from a single 5 mL blood sample						Female: ~266.5 mL ^a Male: ~ 261.5 mL ^a
^a If additional pharmacokinetic/pharmacodynamic and/or safety analysis is necessary, additional blood (up to 50 mL) may be obtained. Note: never to exceed 50 mL.						

Panel D	Pre-study	Treatment Periods	Post-study	Total Collections	mL Per Collection	Total mL/ Test
Laboratory Safety Tests	1	5	1	7	5	35
HIV/Hepatitis Screen (at the discretion of the investigator)	1*			1	5	5
Serum βHcg (if applicable)	1*		1	1	5	5
FSH (if applicable)	1*			See footnote	-	-
PT aPTT	1	5	1	7	5	35
Mixed Venous Oxygen		8		8	5	40
Blood for Planned Genetic Analysis		1		1	8.5	8.5
Blood for MK-5475		27		27	6 mL	162
* Pre-study HIV/Hepatitis Screen, FSH and Serum HcG will be assayed from a single 5 mL blood sample						Female: ~290.5 mL ^a Male: ~ 285.5 mL ^a
^a If additional pharmacokinetic/pharmacodynamic and/or safety analysis is necessary, additional blood (up to 50 mL) may be obtained. Note: never to exceed 50 mL.						

10.9 Appendix 9: Algorithm for Assessing Out of Range Laboratory Values

For all laboratory values obtained at prestudy (screening) visit and/or predose evaluation:

- A. If all protocol-specified laboratory values are normal, the participant may enter the study.
- B. If a protocol specified laboratory value is outside of the parameter(s) outlined in the inclusion/exclusion criteria (including a repeat if performed), the participant will be excluded from the study.
- C. If ≥ 1 protocol-specified laboratory value not specified in the inclusion/exclusion criteria is outside the normal range, the following choices are available:
 1. The participant may be excluded from the study;
 2. The participant may be included in the study if the abnormal value(s) is not clinically significant (NCS) (the investigator must annotate the laboratory value "NCS" on the laboratory safety test source document).
 3. The participant may be included in the study if the abnormality is consistent with a pre-existing medical condition which is not excluded per protocol (eg, elevated eosinophil count in a participant with asthma or seasonal allergies), the medical condition should be annotated on the laboratory report.

OR

4. The abnormal test may be repeated (refer items a. and b. below for continuation of algorithm for repeated values).
 - a. If the repeat test value is within the normal range, the participant may enter the study.
 - b. If the repeat test value is still abnormal, the study investigator will evaluate the potential participant with a complete history and physical examination, looking especially for diseases that could result in the abnormal laboratory value in question. If such diseases can be ruled out, and if the abnormal laboratory value is not clinically relevant, then the participant may enter the study.
- D. If there is any clinical uncertainty regarding the significance of an abnormal value, the participant will be excluded from the study.

10.10 Appendix 10: Hemodynamic Stopping Criteria

Hemodynamic stopping criteria

Individual stopping criteria

During any of the treatment periods, if a particular participant demonstrates a **sustained change** (defined below) in any *one* of the following parameters, that participant will not participate in additional dose escalation. For assessing change from baseline, post-dose values will be compared to the Day 1 predose baseline established by 3 semi-recumbent measurements of heart rate and blood pressure obtained ~1-2 minutes apart within 3 hours prior to dosing.

Participants meeting individual hemodynamic stopping criteria may be re-challenged in this study only after consultation or discussion between the primary investigator and the sponsor.

During any of the treatment periods if a particular participant demonstrates change in any *one* of the following parameters lasting ≥ 90 minutes, dose escalation in that participant will be halted and the participant may be withdrawn from the study or re-challenged at the same dose or at a lower dose. Participants that meet criteria listed below will be followed up until parameters no longer meet stopping rule criteria. Each participant will individually define his limit for continuation. Stopping rules will apply for a particular participant when he demonstrates a **sustained change** (at least 4 triplicate measurements or at least 1 triplicate measurement every 30 min of which the median result of each triplicate measurement will account for checking the stopping criteria) of ≥ 90 minutes in any *one* of the following criteria during the postdose period:

Heart rate:

- 1) Resting HR increase over the predose baseline of ≥ 25 bpm.
- 2) Resting HR > 120 bpm

Blood pressure:

- 1) Resting SBP reduction > 25 mmHg over the predose baseline.
- 2) Resting SBP < 90 mmHg or participant placed in the Trendelenburg position.
- 3) Resting SBP ≥ 180 mmHg
- 4) Resting DBP < 50 mmHg or DBP ≥ 110 mmHg

Blood pressure and heart rate:

- 1) For any participants: > 20 mmHg drop in resting SBP and > 20 bpm rise in resting HR
- 2) For any participants: > 30 mmHg drop in orthostatic SBP and > 30 bpm rise in orthostatic HR

Definitions for HR and BP

Participants must be resting and semirecumbent for *at least* 10 minutes prior to obtaining *any* measurements used to limit dose escalation (except for changes noted while obtaining orthostatic signs).

Baseline HR and BP: Predose baseline values will be determined for each specific period. For the investigator, the baseline will be calculated using the median from the triplicate measurements obtained approximately 1-2 minutes apart within approximately 3 hours prior to dosing to determine that change from baseline. For all formal statistical testing, the mean baseline will be used to calculate the change from baseline.

Sustained changes are defined as lasting greater than or equal to 90 minutes. If any of the resting, semi-recumbent or orthostatic parameters defined above are exceeded, that participant must remain resting and semi-recumbent for at least the next 90 minutes. During that time, BP (systolic and diastolic) and HR will be obtained every 30 minutes (i.e., at 30, 60, and 90 minutes following). If a participant's BP (systolic *or* diastolic), *or* heart rate exceeds the parameters for the median of *all three* of the following three 30-minute periods, this is defined as a sustained finding, and dosing will end for that particular participant. Following 90 minutes, if, in the opinion of the investigator, the participant requires further observation, the participant will remain resting and semi-recumbent until HR and/or BP return to baseline. For HR and BP that are out of range, if the recheck is within normal range this is not considered a sustained change.

Notes

If an assessment of the present and previous periods raises safety and tolerability concerns though individual participant/participants do *not* meet the criteria described above, and after discussion with the investigator and the Merck monitor, dose escalation for the entire panel may end.

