Weight	X													X	period. See section 8.3.1 for PE, height and weight procedures and 8.11.5 for timing window.
Heart Rate(HR) & Blood Pressure(BP)	X		X				X	X	X		X	X	X	X	Pre-dose measure is prior to each period. See section 8.3.2 for all appropriate vital sign procedures and 8.11.5 for timing window.
Orthostatic Vital Signs (HR & BP)	X		X								X		X	X	
Body Temperature(Temp)	X		X								X		X	X	
Respiratory Rate (RR)	X		X				X	X	X		X	X	X	X	
12-lead ECG	X		X				X	X	X		X	X	X	X	Pre-dose measure is prior to each period. See section 8.3.3 for ECG procedure details and 8.11.5 for timing window.

Study Period	Screening			Intervention (Panel A: Part 1, Periods 1-3) (Panel B, C and D: Part 2, Period 1)												Notes
	≤ 35 days pre-randomization	≤ 7 days pre-randomization	Day 1	Hours												
Scheduled Hour, Day	Screening 1	Screening 2	Pre-dose	0	~0.1 (5min)	0.25 (15min)	0.5 (30min)	1	2	3	4	8	24	Post Study ~14 days		
Pulmonary Function Tests (PFTs)	X		X						X				X	X	Pre-dose measure is prior to each period. See section 8.3.5 for specific parameters to be performed at screening and pre / post-dose and 8.11.5 for timing window.	
Serum β-Human Chorionic Gonadotropin (β-hCG; WOCBP only)	X													X		
Urine Pregnancy Test (WOCBP only)			X												Pre-dose measure is prior to each period	
Serum Follicle Stimulating Hormone (FSH) - (WONCBP only)	X															
Echocardiogram (if needed, for Panel B or C participants only)	X														Follow site SOP for assessment of PAH in newly diagnosed participants in Panel B, C or D only	
HIV, hepatitis B and C screen (per site SOP)	X															

Study Period	Screening			Intervention (Panel A: Part 1, Periods 1-3) (Panel B, C and D: Part 2, Period 1)												Notes
	≤ 35 days pre-randomization	≤ 7 days pre-randomization	Day 1	Hours												
Scheduled Hour, Day	Screening 1	Screening 2	Pre-dose	0	~0.1 (5min)	0.25 (15min)	0.5 (30min)	1	2	3	4	8	24	Post Study ~14 days		
Urine/Blood Drug Screen (UDS/BDS) (per site SOP)	X		X												Screening and Period 1 UDB/BDS is mandatory, any additional UDS/BDS are conducted per site SOP	
Hematology/Chemistry	X		X										X	X	See Appendix 2 for laboratory tests	
Urinalysis	X		X										X	X		
PT/aPTT	X		X										X	X		
AE/SAE review	X	X	X-----X											X	See all sections under 8.4	
Phone Call for AE/SAE review														X	Panel A participants that go into Part 2 will have a phone call only 14 days after last dosing period.	
Pharmacokinetics																

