8.3.2.1 Resting Vital Signs

Vital Sign Measurements (Heart Rate and Blood Pressure)

Participants should be resting in a semi-recumbent OR supine position for at least 10 minutes prior to having vital sign (VS) measurements obtained. Semi-recumbent OR supine vital signs (VS) will include heart rate (HR) and blood pressure (BP). The correct size of the BP cuff and the correct positioning on the participants' arm is essential to increase the accuracy of BP measurements. Position used for participants should be consistent across the study.

Predose heart rate (HR) and blood pressure (BP) will be triplicate measurements, obtained at least 1-2 minutes apart within 3 hours of dosing of study drug in Parts 1 and 2 all periods. The median of these measurements will be used as the baseline to calculate change from baseline for safety evaluations (and for rechecks, if needed). Screening, post-dose and post-study HR and BP measurements will also be done in triplicate measurements, obtained at least 1-2 minutes apart.

In Part 1, Periods 1-3 and Part 2, Period 1, participants will continue to rest semi-recumbent from dosing until 4 hours postdose except to stand for the measurement of orthostatic vital signs (VS) (if needed) or other study-related procedure.

Body Temperature

The same method must be used for all measurements for each individual participant and should be the same for all participants.

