8.3.2.3 Orthostatic Vital Signs

In Part 1, Periods 1-3 and Part 2, Period 1, orthostatic vital signs (VS) (HR and BP) will also be obtained. Participants should be semi-recumbent for at least 10 minutes and then stand upright for 2 minutes prior to measurement of orthostatic VS.

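### The orthostatic stopping criterion in Appendix 10 can start rest and rechecks but cannot stop dosing on its own, because every confirming recheck is semi-recumbent

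*Combined protocol and SAP*

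**What the plan says.** Appendix 10 (Section 10.10) sets individual hemodynamic stopping criteria. Under the heading for blood pressure and heart rate it includes more than a "30 mmHg drop in orthostatic SBP and > 30 bpm rise in orthostatic HR".

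Every criterion must be a sustained change of at least 90 minutes. The evidence is either at least four triplicate measurements or "at least 1 triplicate measurement every 30 min", judged on the median of each triplicate. For a participant who meets one, the appendix says "that participant will not participate in additional dose escalation", and re-challenge needs discussion between investigator and sponsor. Its later definition of a sustained finding goes further and ends that participant's dosing.

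The definitions then fix the procedure after a trigger. If resting, "semi-recumbent or orthostatic parameters defined above are exceeded, that participant must remain resting and semi-recumbent for at least the next 90 minutes". Blood pressure and heart rate are taken at 30, 60 and 90 minutes during that rest. The finding is sustained only if the median is out of range at all three; a recheck back in range cancels it.

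Three other places bear on posture and timing:

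- Section 8.3.2.3: participants are semi-recumbent for 10 minutes, "then stand upright for 2 minutes prior to measurement of orthostatic VS".
- Section 8.3.2.1: in Part 1 and in Part 2 Period 1, participants "rest semi-recumbent from dosing until 4 hours postdose except to stand for the measurement of orthostatic vital signs (VS) (if needed").
- Section 1.3: the schedule row that begins "Orthostatic Vital Signs (HR & BP" has postdose marks at 4 h and 24 h only.

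**The concern.** A listed stopping criterion should be capable of being met by the measurements the protocol prescribes. Here the trigger is a standing value and the confirmation is a series of semi-recumbent values. A participant with a large, purely postural response that settles on lying back would be recorded as having no sustained change, so the formal bar on escalation and the clause ending dosing would not apply.

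The matter is relevant to this drug. MK-5475 is a vasodilator. Section 2.2.1 names systemic hypotension as the limiting problem of existing therapies, Section 2.2.2 reports postural dizziness in two healthy participants, and Section 4.3.2 accepts that higher systemic exposure may produce hemodynamic changes. Section 6.6.1 points to Appendix 10 for its pre-specified hemodynamic limits.

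**Working it through.** The plan gives no figure to reproduce. The check traces the rule and then its timing.

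1. **What confirmation needs.** Out-of-range medians at 3 of 3 rechecks (30, 60, 90 minutes), per Appendix 10.

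2. **What the rechecks can supply.** All three fall inside the mandatory semi-recumbent period. An orthostatic value requires 2 minutes upright (Section 8.3.2.3). Orthostatic rechecks prescribed: 0 of 3.

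3. **Does the parenthesis in Appendix 10 help?** The text "except for changes noted while obtaining orthostatic signs" qualifies only the requirement for 10 minutes of rest before any measurement used to limit escalation. It shows that orthostatic changes were meant to limit escalation, but it waives neither the 90-minute test nor the posture during it.

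4. **Does the allowance to stand in Section 8.3.2.1 help?** It belongs to the general rest from dosing to 4 h and is not repeated in Appendix 10. Rechecks come at trigger time t + 0.5, t + 1.0 and t + 1.5 h:
   - 4 h reading: 4.5, 5.0 and 5.5 h.
   - 24 h reading: 24.5, 25.0 and 25.5 h.
   - Falling at or before 4 h: 0 of 6.
   - With the windows in Section 8.11.5 (15 minutes for the 4 h reading, 1 h for the 24 h reading), the earliest first rechecks are 3.75 + 0.5 = 4.25 h and 23 + 0.5 = 23.5 h. Still none.
   - All three rechecks fall within 4 h only if t + 1.5 ≤ 4, that is t ≤ 2.5 h, which means an unscheduled reading. Even then Appendix 10 prescribes no standing recheck.

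5. **Can the scheduled orthostatic readings supply the evidence?** There are two postdose time points, 24 − 4 = 20 h apart. They give neither a triplicate every 30 minutes nor four triplicates.

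6. **Alternative reading: apply the 30/30 limits to the semi-recumbent rechecks.** This takes change against the predose baseline, as Appendix 10 does. A systolic fall above 30 mmHg already exceeds the resting limit of more than 25 mmHg. A heart-rate rise above 30 bpm already exceeds the resting limit of 25 bpm or more. Together they exceed the combined resting limit of more than 20 mmHg with more than 20 bpm. Any participant stopped this way would be stopped by a resting criterion anyway.

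On either reading, the orthostatic criterion produces no stopping event that the resting criteria do not already produce from the same rechecks.

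**The case against.** The strongest defence is that Appendix 10 describes a coherent two-stage rule. An orthostatic signal starts supervised rest, and dosing ends if the change persists at rest. Whether a purely postural response should stop dosing is a clinical choice, and the appendix says openly that a value back in range on recheck is not sustained.

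Part of this stands. The trigger has real value: after 4 h the next scheduled resting heart rate and blood pressure are at 8 h (Section 1.3), so the 30/60/90-minute series may catch a resting breach that would otherwise go unmeasured. A reader might infer that the criterion does nothing at all. The documents do not support that; only its independent stopping effect is missing. But the two-stage reading does not rescue it as a listed stopping criterion, and the parenthesis on orthostatic signs suggests more than a trigger was intended.

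A reader might also infer that participants with an orthostatic response are unprotected. That is not supported either:

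- The resting criteria catch any fall that persists at rest.
- Escalation decisions are joint (Section 6.6).
- Individual safety is reviewed before Panels C and D move on (Section 4.1), and vital signs and adverse events are reviewed before Periods 2 and 3 (Section 8.11.2).
- The investigator may discontinue a participant for any untoward effect (Section 7.1).
- Additional safety evaluations are allowed (Section 8), and urgent ones take precedence (Section 8.11.5).
- The Notes to Appendix 10 let escalation end for a whole panel even when no individual criterion is met.

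Finally, making all three rechecks standing ones would be a heavy remedy. Triplicates at least 1–2 minutes apart (Section 8.3.2.1) would mean 3 × 3 = 9 readings, with roughly 2 + 2 × 1 = 4 to 2 + 2 × 2 = 6 minutes upright each time, in participants who have just had a large orthostatic fall. That objection is sound and shapes the fix below.

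**Conclusion.** Wrong as written, and minor. The criterion is listed as a stopping rule, but the confirmation procedure beside it provides 0 of the 3 standing rechecks that confirmation would need. It operates only as a trigger.

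The consequence is narrow. Orthostatic readings are scheduled only in Part 1 Periods 1–3 and Part 2 Period 1. The remaining planned upward step is in Panel C, from 300 to 360 µg, and Section 4.3.3 already describes doses up to 360 µg in Panels B and C in the past tense. Panel D goes from 480 down to 120 µg, so there only the clause ending dosing would matter. No endpoint, analysis or sample size is affected.

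The conclusion rests on the plain text of Appendix 10, on the definition of an orthostatic reading in Section 8.3.2.3, and on reading the schedule's postdose marks by column position as 4 h and 24 h. How many participants would be affected cannot be estimated from the documents.

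**What to change.** In the definitions of Appendix 10, keep the semi-recumbent rechecks at 30, 60 and 90 minutes. Add that, after an orthostatic trigger, one repeat orthostatic measurement (2 minutes standing, per Section 8.3.2.3) is taken at the end of the 90-minute rest when clinically safe. State that the orthostatic criterion is met if that reading still exceeds both the 30 mmHg and the 30 bpm limits, or if standing is judged unsafe because of symptoms or low blood pressure. State also that, for this criterion, the repeat standing reading replaces the requirement for three out-of-range semi-recumbent medians; otherwise the contradiction remains.

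The cost is two or three sentences and one supervised standing measurement, in triggered participants only, with no new visits. Slightly more participants may meet an individual stopping criterion.
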